3 OBJECTIVES AND ENDPOINTS

Table 2 - Objectives and endpoints

Objectives	Endpoints
Primary 
To evaluate the effect of BIVV020 on the durability of platelet response in participants with persistent/chronic immune thrombocytopenia (ITP)	
Naïve participants: Proportion of participants with a platelet count $\geq 50 \times 10^9/L$ at $\geq 50\%$ of scheduled visits, or for participants with baseline platelet count $< 15 \times 10^9/L$, a $\geq 20 \times 10^9/L$ increase in platelet count from baseline at $\geq 50\%$ of scheduled visits, without receiving rescue ITP therapy, as assessed from Week 3 to Week 24.Participants who previously received sutmilimab: Proportion of participants with maintenance of platelet count $\geq 30 \times 10^9/L$ at $\geq 50\%$ of scheduled visits, without receiving rescue ITP therapy, as assessed from Week 3 to Week 24.
Secondary 
To assess the safety and tolerability of BIVV020To assess the pharmacokinetics (PK) of BIVV020To assess the response rate of treatment with BIVV020To assess the time to responseTo assess the effect of treatment with BIVV020 on the requirement for rescue ITP therapyTo assess the immunogenicity of BIVV020	
Standard clinical and laboratory parameters and adverse eventsPlasma concentrations of BIVV020Response rate at Weeks 24 and 52, defined as a platelet count $\geq 50 \times 10^9/L$ and a greater than 2-fold increase from baseline, measured on 2 occasions at least 7 days apart, with the absence of bleeding (bleeding is defined as bleeding with a score ≥ 2 on the WHO bleeding scale), and the lack of combination ITP therapy during this period.Time from baseline to first platelet response, defined as greater than or equal to each of the following values: $50 \times 10^9/L$ and $100 \times 10^9/L$ (confirmed by 2 measurements at least 7 days apart)Proportion of participants who did not require rescue therapy for an acute episode of thrombocytopenia after Week 3Incidence and titer (if relevant) of anti-BIVV020 antibodies

Objectives	Endpoints
Exploratory	

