9.3.2 Primary endpoint

The primary endpoint is described in [Section 3](#).

The number and proportion of participants meeting the responder criteria will be presented; the 95% confidence interval of the proportion of responders will be estimated using Clopper-Pearson method. Missing data will not be imputed in the statistical analysis. If a patient discontinues study treatment prior to Week 3, the patient will be considered as a non-responder. If a patient discontinues the study treatment after Week 3 and prior to Week 24, his or her responder status will be assessed using the available data between Week 3 and Week 24.

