#### *Observation period*

The observation period will be divided into 3 segments:

- The **pre-treatment period (or the screening period)** is defined as the period from the time of the signing of the informed consent form (ICF) to the first IMP administration.
- The **on-treatment period** is defined as the period from the first IMP administration to the last IMP administration +7 days.
- The **post-treatment period** is defined as the period after the on-treatment period.

The **treatment-emergent** (TE) period includes both on-treatment period and post-treatment period.

Analyses of safety will be based on the treatment-emergent period.

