### **4.3 PRIMARY ENDPOINT(S) ANALYSIS**

The primary endpoint is the proportions of participants who met the following criteria:

1. For naïve participants,
  - a platelet count  $\geq 50 \times 10^9/L$  OR
  - a  $\geq 20 \times 10^9/L$  increase from baseline if baseline platelet count  $< 15 \times 10^9/L$  at  $\geq 50\%$  of scheduled visits from Week 3 to Week 24.

For switchers, a platelet count  $\geq 30 \times 10^9/L$  at  $\geq 50\%$  of scheduled visits from Week 3 to Week 24.

2. No concomitant ITP therapy from Week 3 to Week 24.

Concomitant medications are defined in [Section 5.3](#). The ITP therapies will be identified by the Sanofi coding group, reviewed by medical, and defined in the programming specifications. The ITP therapies include corticosteroids, thrombopoietin receptor agonists, intravenous immunoglobulin, anti-D immunoglobulin, rituximab, fostamatinib, immunosuppressants (azathioprine, cyclosporin A, mycophenolate mofetil), cyclophosphamide, dapsone, danazol.

The response rate will be summarized for naïve participants, switchers, and total for the ITT along with the 95% exact Clopper-Pearson Confidence Interval (CI).

Platelet counts will be summarized by visit. These plots will also be provided:

- Individual platelet count profile: line plot of platelet count by visit for each participant

- Spaghetti plot platelet count by participant
- Median platelet count/change from baseline with by visit

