### ***Prior or concomitant medications***

All medications will be coded using the World Health Organization-drug dictionary (WHO-DD) using the version currently in effect at Sanofi at the time of database lock.

- Prior medications are those the participant used prior to first IMP intake. Prior medications can be discontinued before first administration or can be ongoing during treatment period.
- Concomitant medications are any interventions received by the participant concomitantly to the IMP during the on-treatment period.
- Post-treatment medications are those the participant took in the period running from the end of the concomitant medications period up to the end of the study.
- A given medication can be classified as a prior medication and/or as a concomitant medication and/or as post-treatment medication. If it cannot be determined whether a given medication was taken prior or concomitantly or post, it will be considered as prior, concomitant, and post-treatment medication.

The prior, concomitant, and post-treatment non-ITP medications will be summarized for the ITT population, by anatomic and therapeutic level. The summaries will be sorted by decreasing frequency of anatomic category (ATC) based on incidence in intervention group. Therapeutic classes are sorted by decreasing frequency within each anatomic class. In case of equal frequency, alphabetical order will be used. Participants will be counted once in each ATC category (anatomic or therapeutic) linked to the medication.

Prior ITP, concomitant non-rescue ITP, and concomitant rescue ITP therapies/medications will be summarized separately by the ATC level 4 chemical class and medication name. All ITP therapies will be listed with rescue ITP therapies flagged.

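### As written, the SAP's ITP-therapy criterion for the primary endpoint misses rescue given more than 7 days after the last BIVV020 dose, even when it falls within Week 3 to Week 24

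*SAP*

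**What the plan says.** The endpoint text in protocol Table 2, repeated in SAP Table 1, requires the platelet response "without receiving rescue ITP therapy, as assessed from Week 3 to Week 24". It sets no on-treatment limit on that condition.

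SAP 4.3 turns this into criterion 2: "No concomitant ITP therapy from Week 3 to Week 24". The text that follows begins "Concomitant medications are defined in" and points to SAP 5.3, which states: "Concomitant medications are any interventions received by the participant concomitantly to the IMP during the on-treatment period". In SAP 4.1 the on-treatment period "is defined as the period from the first IMP administration to the last IMP administration +7 days". Whatever comes later belongs to another class: "Post-treatment medications are those the participant took in the period running from the end of the concomitant medications period".

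Protocol 9.3.2 treats early stoppers in two ways. "If a patient discontinues study treatment prior to Week 3, the patient will be considered as a non-responder". For a participant who stops between Week 3 and Week 24, "his or her responder status will be assessed using the available data between Week 3 and Week 24". SAP 4.3 adds no rule for stopping treatment, and SAP 5.2 declares no change to the protocol-planned analyses.

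Protocol 9.3.1 separately defines the efficacy period as first dose to last dose plus 7 days.

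**The concern.** The primary objective is durability of platelet response. A participant who responds, stops BIVV020 and then needs rescue before Week 24 has not met the endpoint as worded. Followed literally, the SAP's definitions place that rescue in the post-treatment class, where criterion 2 does not look.

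Scoring then depends on the order of events. Rescue given while BIVV020 continues fails the criterion. The same rescue given 8 or more days after the last dose does not. With about 12 participants, one such case visibly changes the reported rate.

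**Working it through.** The documents give no power calculation or target rate to reproduce. The check traces the definitions and then counts days and visits.

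**1. Definition chain.** Criterion 2 (SAP 4.3) → concomitant means on-treatment (SAP 5.3) → on-treatment ends at last dose + 7 days (SAP 4.1). Therapy started by that day is caught. Therapy whose timing cannot be determined is counted in all three classes (SAP 5.3), so it is caught too. Only therapy known to fall later escapes.

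**2. Days not covered.** Day = 7 × week + 1, so Week 3 is Day 22 and Week 24 is Day 169. The window is 169 − 22 + 1 = 148 days. Days outside criterion 2 = 169 − (last dose day + 7).

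| Last dose | On-treatment ends | Days outside criterion 2 | Share of 148 |
|---|---|---|---|
| Week 8, Day 57 | Day 64 | 169 − 64 = 105 | 71% |
| Week 10, Day 71 | Day 78 | 169 − 78 = 91 | 61% |
| Week 12, Day 85 | Day 92 | 169 − 92 = 77 | 52% |
| Week 16, Day 113 | Day 120 | 169 − 120 = 49 | 33% |

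**3. Can such a participant still reach 50% of visits?** The platelet row of the protocol's schedule of activities is broken in the text available, so both readings are shown. Neither document says whether the denominator is all scheduled visits or only those with data.

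- Ten visits (SAP 1.1: counts at every on-site visit): Weeks 3, 4, 5, 6, 8, 10, 12, 16, 20, 24. Five are needed, and Weeks 3, 4, 5, 6 and 8 supply them, so 5/10 is reached by Week 8.
- Eight visits (the row read literally, without Weeks 3 and 5): four are needed, and Weeks 4, 6, 8 and 10 supply them, so 4/8 is reached by Week 10. SAP Table 6 targets Day 80 for Week 10 where the weekly arithmetic gives Day 71. If a Day 71 count were lost to that window, Week 12 would be the fourth visit.
- Available visits only: one qualifying visit suffices (1/1). That low bar comes from the available-data rule. The same participant without later rescue would also score as a responder, so it is not evidence for this point.

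The path is therefore open under either denominator.

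**4. Effect of one case.** Exact Clopper-Pearson 95% intervals, with assumed responder counts:

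- Total of 12: 6/12 = 50.0% (21.1 to 78.9) under the literal rule; 5/12 = 41.7% (15.2 to 72.3) if the rescued participant is a non-responder. The difference is 1/12 = 8.3 points.
- Subgroup of 6 (assumed size): 3/6 = 50.0% (11.8 to 88.2) becomes 2/6 = 33.3% (4.3 to 77.7), a difference of 1/6 = 16.7 points.

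**The case against.** The best defence is that the SAP follows the protocol. Protocol 9.3.1 ends the efficacy period at last dose + 7 days, so a rescue check that stops there is consistent with it, and whether to assess response only while on treatment is partly a choice of estimand. This stands to the extent that the SAP is not simply at odds with the protocol. The protocol's endpoint text and its efficacy period pull against each other, and the SAP's wording settles the matter without saying so.

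One can also say that the words Week 3 to Week 24 in criterion 2 already set a calendar window. SAP 4.4 lends some support: it names an on-treatment limit where it wants one, and lists Week 24 separately from the end of the on-treatment period. That may be the intention. But the text below criterion 2 sends the programmer to the on-treatment definition, so it should be made explicit.

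Four stronger readings might be inferred, and the documents do not support them:

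- **That the overall response rate is biased upward.** The word concomitant also fails participants on permitted stable background ITP therapy, which pushes the rate down. The net direction is unknown.
- **That counts raised by the new therapy will add to response.** SAP 4.3 sets no on-treatment limit on counts, but few such counts are planned. After permanent discontinuation, protocol 7.1.1 provides 22 weeks of follow-up with end-of-study procedures at the final visit. For a last dose at Week 3 or later that visit falls at Week 25 or later. Only an early discontinuation visit, visits agreed individually under protocol 7.2 or unscheduled counts could contribute.
- **That any new ITP drug after stopping is failure under the endpoint text.** That text names rescue only. Protocol 6.8.1 ties rescue to acute episodes of thrombocytopenia or bleeding, or to raising a concomitant ITP drug to prevent or treat bleeding. A routine switch after stopping for an adverse event is not clearly rescue.
- **That criterion 2 should therefore cover every ITP therapy in the window.** This would fail participants on unchanged, permitted background therapy and go beyond the endpoint.

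Finally, the study is small and descriptive, protocol 7.1.1 expects permanent discontinuation to be rare, and the planned listings, individual platelet profiles and discontinuation summaries would make a case visible. That limits the harm but does not settle how the participant is scored.

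**Conclusion.** The point holds in a limited form. Applied literally, SAP 4.3 criterion 2 can score as a responder someone who stopped BIVV020 after Week 3 and received rescue ITP therapy more than 7 days after the last dose but before Week 24. The endpoint text makes that person a non-responder. Protocol 9.3.1 shares the tension and has to be reconciled with the endpoint text.

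Each case moves the total by about 8 points among 12 participants. The number of cases cannot be derived from the documents and may be zero. The conclusion rests on reading concomitant as SAP 5.3 defines it and on protocol 9.3.2 keeping these participants evaluable. It does not depend on the denominator or on counts taken after stopping.

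**What to change.** In SAP 4.3 criterion 2, replace concomitant ITP therapy with rescue ITP therapy as defined in protocol 6.8.1, dated from Week 3 to Week 24, whether classed as concomitant or post-treatment and whether or not BIVV020 has been stopped. Score participants with such therapy as non-responders. State that unchanged, permitted background ITP therapy does not count as failure.

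Add that only platelet counts up to last dose + 7 days can count towards response, in line with SAP 4.4 and protocol 9.3.1. State as well that the rescue condition runs over the full calendar window despite that efficacy period, so that the two protocol statements are reconciled.

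The cost is a few sentences and a date-based programming rule. The data should largely exist: protocol 6.8 requires all medication during the study to be recorded, follow-up after permanent discontinuation lasts 22 weeks, and SAP 5.3 lists all ITP therapies with rescue flagged. Rescue after a participant leaves follow-up would still be missed. The response rate may become slightly less favourable.

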#### **4.4 SECONDARY ENDPOINT(S) ANALYSIS**

Participants will continue to receive BIVV020 until the last participant enrolled has completed 52 weeks of treatment. Week 52 is not a scheduled visit and therefore replaced by Week 56 for secondary endpoint(s) analysis. All available data up to Week 56 during the on-treatment period will be included.

The key secondary endpoints include:

##### **The proportion of participants who met the following criteria at Week 24/Week 56:**

1. A platelet count  $\geq 50 \times 10^9/L$  and a greater than 2-fold increase from baseline, measured on 2 occasions at least 7 days apart.
2. No bleeding while the platelet counts are maintained above the threshold. Bleeding is defined as bleeding with a score  $\geq 2$  on the World Health Organization (WHO) bleeding scale ([Section 5.5](#)) collected in the eCRF.
3. No concomitant ITP therapy while the platelet counts are maintained above the threshold.

The response rate will be summarized at Week 24 and Week 56 separately for the ITT along with the 95% exact Clopper-Pearson CI.

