6.8 CONCOMITANT THERAPY

Any medication or vaccine (including over the counter or prescription medicines, vitamins, and/or herbal supplements, and rescue medication) that the participant is receiving at the time of enrollment or receives during the study must be recorded along with:

- Reason for use
- Dates of administration including start and end dates
- Dosage information including dose and frequency

Vaccinations such as seasonal influenza vaccines and other recommended vaccines and booster vaccinations are permitted as per local standard of care, investigator discretion, and local labels.

Concurrent administration of ITP medications (corticosteroids, IVIg, azathioprine, danazol, cyclosporine A, mycophenolate mofetil, or thrombopoietin receptor agonists) is acceptable provided the patient has been on a stable dose for at least 1 month. This applies for both new patients and patients who were previously receiving sutimlimab in Study TDR16218.

Corticosteroids, thrombopoietin receptor agonists, and IVIg are permitted, if the following requirements are met:

- A) Corticosteroids: the first dose of BIVV020 may be dosed only ≥ 4 days after a steroid pulse (single dose of >0.5 mg/kg prednisone equivalent or an increase in prednisone equivalent dose from prior levels) for acute ITP treatment
- B) Thrombopoietin receptor agonists: If receiving weekly thrombopoietin receptor agonist dosing, the last dose must have been administered ≥ 7 days before the first dose of BIVV020. If receiving daily thrombopoietin receptor agonist dosing, the last dose must have been administered ≥ 24 hours before the first dose of BIVV020. Thrombopoietin receptor agonists may be restarted by the Investigator if a participant has an insufficient response to BIVV020.
- C) Intravenous Ig (IVIg): the first dose of BIVV020 must be dosed ≥ 1 day after a dose of IVIg. A single dose of IVIg is allowed during the study; additional doses after the first dose must be approved by the Sponsor.

The Medical Monitor should be contacted if there are any questions regarding concomitant or prior therapy.

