6.8.1 Rescue medicine

Rescue medicines given for acute episodes of thrombocytopenia/bleeding, such as steroid pulse/bolus, thrombopoietin receptor agonists, or platelet transfusion are allowed (see above for guidance on IVIg). Additionally, increasing the dose of concomitant ITP medications to prevent or treat bleeding due to low platelet counts is allowed and would be considered rescue therapy.

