### 1.2 OBJECTIVE AND ENDPOINTS

**Table 1 - Objectives and endpoints**

	Objectives	Endpoints
Primary	

To evaluate the effect of BIVV020 on the durability of platelet response in participants with persistent/chronic immune thrombocytopenia (ITP)

	

Naïve participants: Proportion of participants with a platelet count <math>\geq 50 \times 10^9 / L</math> at <math>\geq 50\%</math> of scheduled visits, or for participants with baseline platelet count <math>< 15 \times 10^9 / L</math>, a <math>\geq 20 \times 10^9 / L</math> increase in platelet count from baseline at <math>\geq 50\%</math> of scheduled visits, without receiving rescue ITP therapy, as assessed from Week 3 to Week 24

Participants who previously received sutmilimab: Proportion of participants with maintenance of platelet count <math>\geq 30 \times 10^9 / L</math> at <math>\geq 50\%</math> of scheduled visits, without receiving rescue ITP therapy, as assessed from Week 3 to Week 24.

Objectives	Endpoints
Secondary 

• To assess the safety and tolerability of BIVV020

• To assess the pharmacokinetics (PK) of BIVV020

• To assess the response rate of treatment with BIVV020

• To assess the time to response

• To assess the effect of treatment with BIVV020 on the requirement for rescue ITP therapy

• To assess the immunogenicity of BIVV020

	

• Standard clinical and laboratory parameters and adverse events

• Plasma concentrations of BIVV020

• Response rate at Weeks 24 and 52, defined as a platelet count <math>\geq 50 \times 10^9 /L</math> and a greater than 2-fold increase from baseline, measured on 2 occasions at least 7 days apart, with the absence of bleeding (bleeding is defined as bleeding with a score <math>\geq 2</math> on the WHO bleeding scale), and the lack of combination ITP therapy during this period.

• Time from baseline to first platelet response, defined as greater than or equal to each of the following values: <math>50 \times 10^9 /L</math> and <math>100 \times 10^9 /L</math> (confirmed by 2 measurements at least 7 days apart)

• Proportion of participants who did not require rescue therapy for an acute episode of thrombocytopenia after Week 3

• Incidence and titer (if relevant) of anti-BIVV020 antibodies

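### The Week 24/56 response rule checks for ITP therapy only while counts are high, so a completed one-off rescue given at a low count can be scored as a BIVV020 response

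*SAP*

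**What the plan says.** SAP 4.4 defines response at Week 24/Week 56 by three criteria. The first is a platelet count of at least 50 × 10⁹/L and more than twice baseline, "measured on 2 occasions at least 7 days apart". The second concerns bleeding. The third is "No concomitant ITP therapy while the platelet counts are maintained above the threshold". The SAP calls this a key secondary endpoint and reports it with an exact Clopper-Pearson interval in the ITT population.

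Protocol section 3 words the therapy condition as "the lack of combination ITP therapy during this period", and SAP Table 1 repeats it. Neither defines the period. SAP Appendix 2 declares no changes to the protocol-planned analyses.

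Three other provisions bear on the rule:

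- **Rescue.** Protocol 6.8.1 says "Rescue medicines given for acute episodes of thrombocytopenia/bleeding, such as steroid pulse/bolus, thrombopoietin receptor agonists, or platelet transfusion are allowed", and also counts dose increases of concomitant ITP drugs as rescue. Protocol 6.8 adds "A single dose of IVIg is allowed during the study".
- **Concomitant medication.** SAP Appendix 3 says "Concomitant medications are any interventions received by the participant concomitantly to the IMP during the on-treatment period". It attaches no carry-over time to a dose that has been completed.
- **Primary endpoint.** SAP 4.3 uses a fixed window that does not depend on the count: "No concomitant ITP therapy from Week 3 to Week 24".

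**The concern.** A therapy condition in a response definition is there to keep the effect of other treatment out of the response. Here the window is opened by the high count itself. A treatment that causes the high count will normally have been given before it. A drug that continues into the high-count spell is caught. A one-off treatment given and finished while the count was low is not.

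The study is open-label with no control arm, so excluding other ITP treatment is the main means by which this endpoint attributes a rise to BIVV020. A missed rescue can only move the rate upward. The same rescue, given between Week 3 and Week 24, could make a participant a non-responder on the primary endpoint and a responder on this one.

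**Working it through.** The plan has no figure that depends on this rule, and the sample size is not determined statistically, so there is nothing to reproduce. Two checks were made.

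**1. The rule applied as written.** Criteria 1 and 3 of SAP 4.4 were applied to invented participants with baseline 10 × 10⁹/L; criterion 2 (bleeding) was assumed met. With that baseline, twice baseline is 20, so the 50 threshold governs. A pair qualifies if two counts at least 7 days apart, and any count between them, are at least 50. The SAP rule then asks whether therapy was given between the first and second count of the pair. Two alternatives were also tried: no ITP therapy from Day 1 to Week 24, and no ITP therapy from an assumed 28 days before the first count through the second.

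| Invented participant | SAP rule | No therapy from Day 1 | 28-day look-back |
|---|---|---|---|
| A: one rescue on Day 24; 90 on Day 29, 62 on Day 36, low otherwise | responder | non-responder | non-responder |
| B: no rescue, sustained rise | responder | responder | responder |
| C: continuous daily therapy | non-responder | non-responder | non-responder |
| D: one rescue on Day 160; only Week 24 high | non-responder | non-responder | non-responder |
| E: one rescue on Day 135; 90 at Week 20, 55 at Week 24 | responder | non-responder | non-responder |

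In A the rescue is 29 − 24 = 5 days before the first qualifying count; in E it is 141 − 135 = 6 days before. Both escape the SAP rule and both fall within the assumed look-back.

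- A counts only if a pair at any time up to Week 24 is acceptable. It also needs a count on Day 36. SAP 1.1 says counts are taken at on-site visits, which are weekly to Week 6, but the platelet row of the protocol's Schedule of Activities appears to skip Day 36 (the table may be imperfectly reproduced). If there is no Day 36 draw, A needs an unscheduled count, or a rise lasting from Day 29 to Day 43, which is 14 days.
- E counts even if the pair must include Week 24, but its rise has to be present at both Day 141 and Day 169, 28 days apart.
- C shows that overlapping therapy is already excluded. D shows that an unconfirmed rise is not a response.

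**2. Weight of one participant at n=12.** One participant is 1/12 = 8.3 percentage points. The exact 95% limits for x responders of n are the 0.025 quantile of Beta(x, n − x + 1) and the 0.975 quantile of Beta(x + 1, n − x).

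| Counted responders | Rate | 95% CI |
|---|---|---|
| 4/12 | 33.3% | 9.9 to 65.1 |
| 5/12 (one rescue-driven) | 41.7% | 15.2 to 72.3 |
| 6/12 (two rescue-driven) | 50.0% | 21.1 to 78.9 |

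The starting value of 4/12 and the number misclassified are assumptions chosen for illustration.

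**The case against.** The case for leaving the rule alone has real content.

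- **Much rescue is already caught.** A thrombopoietin receptor agonist or a raised background dose that continues into the high-count spell disqualifies. This stands: the gap concerns completed one-off treatment only. A reader might infer that the SAP ignores rescue altogether for this endpoint; it does not.
- **Confirmation limits the exposure.** If the pair must include Week 24 or Week 56, scheduled visits are 4 weeks apart before Week 24 and 8 weeks apart before Week 56. Without an unscheduled count, a rescue-driven rise would have to last that long. This stands as a limit, but the SAP does not say that the pair must include those visits, and early visits are much closer together.
- **The SAP may be a fair reading of the protocol.** A reader might infer that SAP 4.4 contradicts "lack of combination ITP therapy during this period". The documents do not support that. The period is undefined and could mean the interval between the two counts. The SAP wording is a permissible but weak reading.
- **Rescue is visible elsewhere.** The primary endpoint bars ITP therapy from Week 3 to Week 24, the rescue-free proportion is reported, rescue therapies are flagged in a listing, and individual platelet profiles are plotted. With about 12 participants each case could be found. That helps a careful reader, but it does not change the reported rate or its interval.
- **Not all 12 are equally exposed.** Up to 6 are participants who responded to sutimlimab and may receive it during screening. The SAP averages pre-dose platelet counts for baseline, so theirs may be raised and the more-than-2-fold condition harder to meet. This is fair, and is one more reason to treat the figures as illustrative.

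**Conclusion.** The point holds in a limited form. As written, criterion 3 lets a completed one-off rescue given at a low count produce a qualifying pair, and no look-back, carry-over or rescue-as-non-response rule in the SAP prevents it. The possible error is in one direction, upward.

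Its size cannot be derived from the documents, which give neither a rescue rate nor a duration of rescue effect. Each case would be worth 8.3 points at n=12. A reader might take the step from 33.3% to 50.0% as an estimate of the bias; it is only what two misclassified participants of 12 would do.

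The risk is greatest if pairs may fall at the closely spaced early visits or use unscheduled counts, and smaller if the pair must include Week 24/56. The conclusion rests on the literal wording of SAP 4.4 and on a rescue effect that lasts at least from one qualifying count to the next. This is a secondary endpoint with no hypothesis test, so the matter should be corrected but does not threaten the primary analysis.

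**What to change.** In SAP 4.4:

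1. Keep the present bar on any concomitant ITP therapy during the above-threshold period.
2. Add that a pair of counts does not qualify if rescue ITP therapy was given, at any time after the first IMP dose, within a pre-specified look-back before the first qualifying count, through the second. Use the Protocol 6.8.1 definition of rescue, including dose increases of background ITP drugs and platelet transfusion; transfusion is not named in the SAP 4.3 list of ITP therapies.
3. Fix the look-back length in advance, for example 28 days, and say that it is an assumption. Vary it in sensitivity analyses, one of which disqualifies any rescue since Day 1.
4. State whether the pair must include Week 24/56.
5. Leave the two time-to-response endpoints as the protocol defines them, without a therapy condition, and add a supplementary analysis in which rescue-affected counts do not qualify as events.

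Three simpler rules are less suitable. Starting the bar at Week 3, as the primary endpoint does, would leave a pair at Day 8 and Day 15 unprotected. Making any rescue since Day 1 the main rule would, at Week 56, fail a participant rescued early who later responded unaided. Replacing the bar on ITP therapy with a bar on rescue only would loosen the protocol's condition; stable background therapy should not be exempted unless the sponsor first reconciles that with "the lack of combination ITP therapy during this period".

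The cost is SAP text and programming; rescue therapies are already flagged in the planned listing. The reported response rate may be slightly lower, and the look-back length remains a convention.
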